## **Section G: Sample Size/Data Analysis**

### **G1. Sample Size**

How many subjects (or specimens, or charts) will be used in this study?

Local: 335      Worldwide: 335

Please indicate why you chose the sample size proposed:

A total of 335 participants will be recruited for this study: 252 Veterans will be recruited to participate in the RCT; 40 Veterans who participated in iCBT and their family members (up to 40) will be invited to participate in the qualitative interview.

For the RCT, a total of 252 patients will be randomized across the 3 arms (95 to iCBT, 95 to sCBT, and 62 to TAU) to have 80% power to detect differences among groups in the primary outcomes. A recent meta-analysis of transdiagnostic treatment for anxiety demonstrated a medium effect size ( $g=.69$ ) on quality of life outcomes. Based on these findings, we are using a more conservative effect size of 0.50 to calculate the sample size that will need to be recruited and randomized to draw conclusions. We will use unequal randomization to the active intervention arms and to treatment as usual to reduce unnecessary recruitment. We also inflated the sample size to account for intraclass correlations among patients and for attrition and loss to follow-up in order to obtain the number that must be recruited for the study. The recruited sample size of 95 for iCBT and 95 for sCBT, assuming 20% attrition at 1 month and accounting for clustering of patients within therapists, will result in 49 patients per group for analysis. For our primary analyses, this sample size will have 80% power to detect a medium effect size of .57 using a two-group t-test with  $\alpha=.05$  two-sided significance level.

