### **G2. Data Analysis**

Provide a description of your plan for data analysis. State the types of comparisons you plan (e.g. comparison of means, comparison of proportions, regressions, analysis of variance). Which is the PRIMARY comparison/analysis? How will the analyses proposed relate to the primary purposes of your study?

For our primary analyses, we will compare changes between the iCBT, sCBT, and TAU groups at all time periods in a single regression using a hierarchical mixed-model analysis. Because the number of patients randomized to the 3 groups is not equal, we will test for unequal variances and if necessary, will account for this in our regression models. For outcomes with unequal variances, in the mixed model, we will estimate the variances separately and adjust the degrees of freedom for the unequal variances. A priori covariates will also be included in the model. A significant time-by-treatment interaction will be followed by pairwise contrasts to determine whether the active interventions differed from TAU and whether the active treatments differed from each other. We will report the p-values and adjust p-values post-hoc using multiple comparisons procedures (e.g., Bonferroni) as recommended in the literature. For secondary analyses, we will run hierarchical linear regression models for each outcome using the baseline and 1 month data and with the a priori covariates. Hierarchical logistic regression models will be used to test differences in treatment engagement across conditions.

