Statistical Methods

Specific Aim 1: Examine the effectiveness of iCBT in improving community reintegration and overall quality of life. Community reintegration will be measured using the 3 subscales of the CRIS-CAT: extent of participation, perceived limitations, and satisfaction with participation. Quality of life will be measured by the SF-12 Physical Component Summary (PCS) and Mental Component Summary (MCS) scores. Although our quantitative analyses will be intention-to-treat, we will provide information on the number of and characteristics of any participants who did not receive the treatment as allocated or who did not complete the study. We will tabulate baseline characteristics, such as age, race, gender, disease severity, comorbidities, and psychotropic medications. Based on recommendations of the CONSORT group,⁸¹ we will adjust analyses for variables we have decided *a priori* may be important to control (i.e., depression, period of service [OEF/OIF/OND, Gulf War, and other] concomitant psychotropic medication use, and the primary diagnosis stratification variable). Results from both an intent-to-treat and treatment completer analyses will be compared.

Hypothesis 1a: *iCBT and sCBT will significantly improve community reintegration and quality of life relative to TAU at 3-and 6-month follow-ups.* To compare changes between the iCBT, sCBT, and TAU groups at all time periods in a single regression, we will use a hierarchical mixed-model analysis. Because the number of patients randomized to the 3 groups is not equal, we will test for unequal variances and if necessary, will account for this in our regression models. For outcomes with unequal variances, in the mixed model, we will estimate the variances separately and adjust the degrees of freedom for the unequal variances. The model will contain terms for the intercept, treatment, time period and interaction between time and treatment. *A priori* covariates as well as the stratification variable of anxiety disorders will also be included in the model. A significant time-by-treatment interaction will be followed by pairwise contrasts to determine whether the active interventions differed from TAU and whether the active treatments differed from each other. We will report the p-values and adjust p-values post-hoc using multiple comparisons procedures (e.g., Bonferroni) as recommended in the literature.⁸²

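### H1a's active-versus-TAU contrasts are opened only by an overall interaction test and then adjusted as well: the gate adds no worst-case error protection, and the stacked rule has less power than a per-visit closed test

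*SAP*

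**What the plan says.** SAP, Statistical Methods, Hypothesis 1a, claims that iCBT and sCBT each improve reintegration and quality of life relative to TAU at 3 and 6 months. The test is one mixed model over all time periods, with treatment, time period and their interaction. The decision rule has two layers:

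- Gate: "A significant time-by-treatment interaction will be followed by pairwise contrasts to determine whether the active interventions differed from TAU" and whether the active arms differ from each other.
- Adjustment: "We will report the p-values and adjust p-values post-hoc using multiple comparisons procedures (e.g., Bonferroni" being the only method named, and only as an example.

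Protocol G2 repeats the rule: "A significant time-by-treatment interaction will be followed by pairwise contrasts". Neither document says what happens if the interaction is not significant; the natural reading is that the contrasts are not tested. Hypothesis 2a applies the same analysis to anxiety and depression, which the SAP calls secondary outcomes.

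Three things are left open: the coding of time (the SAP's missing-data section leaves extra nonlinearity terms to a visual check), the adjustment method, and the family it covers. Protocol G1 gives power for something simpler: "80% power to detect a medium effect size of .57 using a two-group t-test", at a .05 "two-sided significance level". No power is given for the gated, adjusted contrasts against TAU.

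**The concern.** H1a asks whether active treatment beats TAU at two named visits. The gate asks whether the three arms differ in their course over any of the four visits. An outcome with a real 3- or 6-month benefit that narrowly misses the gate would never have H1a tested. An outcome that passes is penalised again by the adjustment.

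Two layers would be justified if each protected against something the other did not. Here the adjustment alone already controls error over the three pairs at a visit, so the gate can only remove findings. At stake is power for the trial's main claim, which names both active arms and so needs both contrasts to succeed.

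**Working it through.** **1. Inputs from Protocol G1.** Randomised: "95 to iCBT, 95 to sCBT, and 62 to TAU". Losses: "assuming 20% attrition at 1 month and accounting for clustering of patients within therapists", giving the stated 49 per active arm. Check: 95 × 0.8 = 76, and 76/49 = 1.55, the implied design effect. TAU with attrition only: 62 × 0.8 = 49.6, taken as 50. Effects: 0.57 SD (the power statement) and 0.50 SD ("we are using a more conservative effect size of 0.50 to calculate the sample size").

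**2. The plan's own figure.** Power ≈ Φ(d√(n/2) − 1.960) = Φ(0.57 × 4.950 − 1.960) = Φ(0.861) = 80.5%; the exact t calculation gives 79.8%. The stated 80% reproduces for one unadjusted test.

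**3. Bonferroni alone.** Three pairs give .05/3 = .0167, critical value 2.394. For 49 versus 50, √(49 × 50/99) = 4.975.

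- 0.57 SD: unadjusted Φ(2.836 − 1.960) = 81%; Bonferroni Φ(2.836 − 2.394) = 67%.
- 0.50 SD: unadjusted Φ(2.487 − 1.960) = 70%; Bonferroni Φ(2.487 − 2.394) = 54%.

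Bonferroni therefore costs about 14 and 16 points before any gate is applied.

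**4. The whole rule, by simulation.** Assumed, not in the documents: categorical time, so the gate has (3 − 1)(4 − 1) = 6 df; equal correlation 0.5 between visits; both active arms d SD better than TAU at 3 and 6 months; at 1 month iCBT already at d and sCBT at d/3. Contrasts are change to 6 months, known-variance approximation.

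Power at 0.57 SD, one active-TAU contrast / both:

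- Gate, then Bonferroni over three pairs: 66% / 52%
- Bonferroni over three pairs, no gate: 67% / 52%
- Holm over three pairs, no gate: 70% / 58%
- Closed test at the visit (2-df three-arm test at .05, then pairs at .05): 77% / 69%

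At 0.50 SD the gated rule has 52% / 37% and the closed test 64% / 55%. The losses against the closed test are thus 77 − 66 = 11 and 69 − 52 = 17 points at 0.57 SD, and 64 − 52 = 12 and 55 − 37 = 18 at 0.50 SD.

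**5. What the gate itself costs.** Under 1 point here at 0.57 SD and about 2 at 0.50 SD. Over most other time patterns and correlations it is about 1 to 3 points. With gradual onset and autoregressive correlation 0.7 it reaches 8.7 points (0.57 SD) and 10 (0.50 SD).

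**6. Sensitivity.** At correlation 0.6 and 0.57 SD: 78% versus 86% for one contrast, 66% versus 81% for both. At 0.69 SD the one-contrast loss is 6.5 to 8 points in most patterns, and the loss for both is 88 − 76 = 12. Time coding matters too: at 0.69 SD, with a steady effect from 1 month on, a linear-time 2-df gate costs about 15 points (equal correlation) or 27 (autoregressive 0.7), against under 1 point for the 6-df gate.

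**7. False claims among the three pairs at one visit.**

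- No arm differs at any visit: gate plus Bonferroni about 1.6%; Bonferroni alone 4.4%; closed test about 5%.
- Arms differ at 1 month only: gate plus Bonferroni 4.3%; closed test 5.0%.
- The same case with the 6-df gate kept and Bonferroni dropped: about 12%.

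Once a 1-month effect opens the gate, the rule falls back to Bonferroni. The gate lowers error only when nothing differs anywhere.

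**The case against.** The strongest reply is that an omnibus test followed by adjusted contrasts is conventional, errs on the safe side, and that Bonferroni is only an example, so Holm or a closed procedure is not excluded. Much of this stands. The rule does not inflate error within a visit, and both 6 df and Bonferroni are readings of an open text. But that openness is itself a reason to settle the rule before analysis, and no choice of adjustment gives the gate a protective role.

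A second reply is that a per-visit closed test buys power with error across visits. This also stands: H1a names two visits, and with no arm differing the false-claim rate over both is 9.1% for the per-visit test at .05, against 2.9% for the gated rule. Applying Holm to the two 2-df tests and then testing pairs at .05 does not cure it. When a true effect makes both 2-df tests reject, the remaining null pair is tested at a full .05 at each visit, and the rate over both is about 8 to 9%. If control across visits is wanted, alpha must be split.

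Three stronger readings are tempting and not supported:

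- That the rule's family-wise error is about 1.5% rather than 5%. That size holds only when nothing differs at any visit.
- That the gate causes the 10- to 18-point loss. Most of it is Bonferroni.
- That Bonferroni is superfluous behind this gate. Step 7 shows it is not.

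**Conclusion.** The point holds as one of efficiency and incomplete specification, not of inflated error. The interaction gate is tied to visits outside H1a, adds no worst-case protection to adjusted contrasts, and can only block true findings. Under the stated assumptions the stacked rule gives up about 10 to 13 points for one active-TAU contrast and 17 to 18 for both against a per-visit closed test, and has only about even odds of showing both at 0.57 SD.

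These sizes rest on assumed correlation, time pattern and contrast family, and on G1's 1-month attrition carried to later visits; they shrink at larger effects. The claim concerns the primary outcomes in H1a; H2a inherits the rule for secondary outcomes only. It is separate from multiplicity across the several outcome scales.

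**What to change.** In SAP Hypothesis 1a (and so 2a) and Protocol G2, remove the significant interaction as a condition for the contrasts, state that time is categorical, and define the family. Then choose one rule:

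- **(a) Closed test at each visit.** At 3 and at 6 months, test the 2-df three-arm difference in change from baseline; if significant, test the three pairs at the same level. With three arms this is an exact closed test, because any two equalities imply that all three arms are equal. Use .05 per visit if control is per visit. If control across both visits is wanted, use .025 per visit for both the 2-df test and the pairs: about 4.5% across visits, with power no lower than the present three-pair rule. Do not use Holm on the two 2-df tests followed by pairs at .05.
- **(b) Direct pairs.** Test the three pairs at each visit without a gate, with Holm in place of Bonferroni: 70% for one and 58% for both at 0.57 SD, with control within a visit.

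G1 should then give the power of the chosen rule against TAU. The cost is a few sentences, with no added patients or data. The downside is that the within-visit false-claim rate under the complete null rises from about 1.6% to at most 5%.

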**Section D: Purpose and Objectives**

The overall objective of the proposed study is to improve reintegration across the lifespan and quality of life in Veterans with anxiety-based disorders including co-occurring depression. A randomized controlled trial will test the effectiveness of transdiagnostic group CBT delivered in an intensive weekend format. This transdiagnostic protocol addresses multiple anxiety-based disorders in a single protocol by incorporating general core components of CBT with additional skills-based modules that can be flexibly tailored to any anxiety disorder. Intensive CBT (iCBT) is an innovative and promising method of treatment delivery with the potential to produce rapid improvement in functional and clinical outcomes. The compressed format (e.g., weekend) of iCBT increases the likelihood that Veterans will engage in and complete treatment. During the course of the study, we will also gather qualitative data from Veterans who participated in the weekend treatment (and their family members) to obtain a deeper understanding of how iCBT and environmental barriers and facilitators have impacted their overall functioning and quality of life.

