#### Treatments

Participants will be randomly assigned to one of three treatment arms (iCBT, sCBT, TAU), described in detail below. Both iCBT and sCBT treatments are identical except for delivery format. Persons delivering the treatment will include a masters-level and doctoral-level interventionist who will be trained to deliver treatments in both intervention conditions under the supervision of [name], a licensed psychologist and co-investigator on this project. [name] is experienced in transdiagnostic treatment for anxiety and in the delivery of exposure-based treatments for anxiety disorders with Veterans. She will work closely with the interventionists to ensure that all patients are closely monitored, with their safety taking priority above the needs of the study. Our pilot work with Veterans at the MEDVAMC and community based outpatient clinics demonstrates the intensive weekend format to be a safe mode of treatment delivery. However, as an added level of precaution, the MEDVAMC has an emergency department with an on-call psychiatrist available 24 hours a day in the unlikely event that a patient needs immediate medical intervention.

**Standard Cognitive Behavioral Treatment:** The sCBT condition consists of 12 treatment sessions delivered once weekly over a 12-week period. Duration of sessions will be approximately 90 minutes, depending on the session module. For example, psychoeducation sessions typically last 60 minutes, whereas cognitive restructuring and exposure sessions typically last up to 90 minutes. Thus, the entire treatment requires approximately 16 hours of direct patient contact. A maximum of 6 Veterans may be enrolled per group cycle. The transdiagnostic treatment protocol consists of (1) psychoeducation about the general treatment structure, the nature of anxiety disorders and co-occurring symptoms such as depression, and physiology underlying the fight/flight response; (2) cognitive restructuring, a method of challenging maladaptive thoughts that maintain negative affect and fears by examining evidence that replaces catastrophizing and overestimations in thinking; and (3) exposure to feared stimuli through imaginal, interoceptive, or in-vivo exercises. Treatment concludes with relapse prevention planning. Homework is completed regularly over the course of treatment. Patients will be asked to monitor and record their anxiety and mood symptoms, complete thought records, and engage in exposure exercises.

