Hypothesis 1b: *iCBT will result in improved reintegration/quality of life measures relative to sCBT at 1-month follow-up.* Only patients in the iCBT and sCBT groups will be used in the analyses. For each outcome, we will run a hierarchical linear regression model using the baseline and 1 month data and with the *a priori* covariates and anxiety disorder stratification variables. Patients will be nested within therapist. The models will contain the 1 month value as the outcome variable and the baseline value of the outcome as an additional covariate. A significant value for the parameter estimate for the intervention will indicate that the iCBT and sCBT groups differed at 1 month.

Specific Aim 2: Examine the effectiveness of iCBT in reducing anxiety/depression symptoms relative to sCBT and TAU. **Hypothesis 2a:** *iCBT and sCBT will significantly reduce anxiety and depression symptoms relative to TAU at 3-and 6- month follow-ups.* The analyses described for hypothesis 1a will be repeated for this hypothesis using the secondary outcomes. Anxiety will be measured using the BAI and depression measured using the BDI-II. **Hypothesis 2b:** *iCBT will result in improved anxiety/depression measures relative to sCBT at 1-month follow-up.* The analyses described for hypothesis 1b will be repeated for this hypothesis using the secondary outcomes.

Specific Aim 3 (Exploratory): Hypothesis 3a: *Compare rates of psychotherapy engagement in iCBT relative to sCBT.* We will use hierarchical logistic regression models to test if the iCBT and sCBT groups differed on treatment engagement (defined as the percentage of randomized patients who participated in 12 or more treatment hours). The outcome will be whether or not

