the patient completed 12 or more treatment hours. The a priori variables to be included as independent variables in the treatment engagement model will be selected based on the SOTA Access model described earlier. Items comprising the subscales of geographical, temporal, financial, and cultural barriers will be selected from the PB-SMHS measure for inclusion. The model will also include intervention group and our primary diagnosis stratification variable. To account for clustering, we will nest patients within therapist. **Hypothesis 3b:** Examine heterogeneity of treatment effects on 3- and 6-month outcomes. Because our sample size may not be adequate to substantiate sources of heterogeneity of treatment effects (HTE), exploratory analyses will allow us to describe patterns that can be examined in future larger trials. We will assess HTE on 3-and 6- month effectiveness outcomes through examining potential moderators collected at baseline including demographics, geographic region, co-occurring depression, psychiatric comorbidity, and medication use. Examining the role of potential moderator variables will provide a better understanding of how individuals vary in their response to iCBT and the conditions under which iCBT may be optimal. Following the approach suggested by Kent et al⁸³ for assessing HTE, we will use a multivariable prediction tool to report how relative and absolute risk reduction varies by baseline risk. We will use an internally-developed model from a regression analysis of data from the active treatment arms. Per Brookes et al⁸⁴, we will test the interaction terms in the models as the most statistically robust approach to assessing HTE.

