Missing Data for quantitative analyses: To assess impact of missing data, we will conduct sensitivity analyses using tests for missing completely at random and tests for nonrandom missingness using approaches suggested by Molenberghs and Kenward.⁸⁵ These will allow us to evaluate whether the reasons for loss to follow-up at the various time periods are related to the observed values of the outcome variables. We will also plot the data over time to visually assess changes in outcomes from baseline to 3 and 6 months and to indicate whether additional terms are needed in the models to account for nonlinearity over time. *We will also follow recommendations provided by Sterne et al.⁸⁶ regarding multiple imputation methods for missing data in clinical research. In performing our imputation techniques, we will assess non-normality of the data and transform variables as needed to approximate normality before imputation and then transform the imputed values back to the original scale. We will attempt to avoid bias in the imputation analyses by including all variables in the substantive analyses and when computationally feasible, all variables predictive of the missing values and all variables influencing the cause of the missing data, even if they are not of interest in the substantive analysis.*

Initial analyses will be intention-to-treat. We will use the PROC MI in SAS software for multiple imputation of the missing data. The Markov chain Monte Carlo method will be used for imputation if the dataset has arbitrary missing data patterns. PROC MIANALYZE will subsequently be used to combine the results of the analyses of imputation to generate valid statistical inferences. In addition to the analyses of imputed data, we will conduct completer analyses on the observed data. *If the results of the completer analyses and analyses based on imputed values differ, we will look for possible reasons and report this in our publications. Sensitivity analyses will investigate the robustness of the findings to be assumed missing not at random (NMAR).*^{87,88}

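### H1b, H2b and H3a allow for clustering by therapist only, although both active arms are delivered in therapy groups of at most six

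*SAP*

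**What the plan says.** SAP, Hypothesis 1b, restricts the analysis to iCBT and sCBT and regresses the 1-month value on treatment, the baseline value, the prespecified covariates and the diagnosis stratum. Its one sentence on clustering is "Patients will be nested within therapist". Hypothesis 2b reuses this model for anxiety and depression. For the engagement model in Hypothesis 3a the SAP writes "To account for clustering, we will nest patients within therapist", with engagement "defined as the percentage of randomized patients who participated in 12 or more treatment hours". Hypotheses 1a and 2a use a hierarchical mixed model for which no cluster level is named.

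On delivery, Protocol Section D states: "A randomized controlled trial will test the effectiveness of transdiagnostic group CBT delivered in an intensive weekend format". Under Treatments in F2, the same limit is set for each active arm: "A maximum of 6 Veterans may be enrolled per group cycle". On staffing, that section says: "Persons delivering the treatment will include a masters-level and doctoral-level interventionist who will be trained to deliver treatments in both intervention conditions".

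Protocol G1 inflates the sample size for intraclass correlation and mentions clustering within therapists, but gives no ICC and no cluster size. G2 classes the 1-month models as secondary: "For secondary analyses, we will run hierarchical linear regression models for each outcome using the baseline and 1 month data". The SAP's missing-data section aims to avoid bias in the imputation by "including all variables in the substantive analyses".

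**The concern.** Patients treated in the same small group share sessions, group dynamics and timing, so their outcomes are likely to be correlated. The sponsor accepts that clustering has to be modelled but names only the therapist, and the therapist term does not do the work of a group term. If each therapist leads groups in both arms, a good or poor therapist shifts both arms alike and largely drops out of the iCBT/sCBT difference. Each therapy group lies wholly within one arm, so its effect stays in the difference. The model would then treat patients within a group as independent, given therapist and covariates.

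If so, the standard error for iCBT against sCBT is too small, confidence intervals are too narrow, and a nominal 5% test rejects too often. The comparison matters more than its secondary label suggests: the 80% power in G1, which is described as applying to the primary analyses, is worked out for iCBT and sCBT with 1-month attrition. For H1a and H2a the gap is only that the cluster level is unstated; an omission is not demonstrated there.

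**Working it through.** **Inputs.** From G1: 95 randomised to each active arm, 20% attrition at 1 month, 49 per arm for analysis, effect size 0.57, 80% power, two-sided alpha 0.05. From F2, Treatments: at most 6 per group. Assumed, because the documents give no value: group ICC 0.02 to 0.15.

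**The plan's own figure.** With 49 per arm and d = 0.57, power is 79.8% (noncentral t, 96 df) or 80.5% (normal approximation), so the stated 80% reproduces. The allowance for clustering is 95 × 0.8 / 49 = 76/49 = 1.55. Its basis is not given. Solving 1 + (m − 1) × ICC = 1.55 gives ICC 0.110 for clusters of 6, 0.145 for clusters of 4.8, or 0.015 for two therapists with 38 analysed patients each.

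**Number and size of groups.** 95/6 = 15.8, so at least 16 groups per arm. A full group after 20% attrition has 6 × 0.8 = 4.8 analysed patients.

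**True error of a test that omits group, therapist crossed with arm.** Design effect DE = 1 + (m − 1) × ICC. True two-sided error = 2 × [1 − Φ(1.96/√DE)]. If only iCBT is clustered, DE is replaced by (DE + 1)/2. For example, with m = 4.8 and ICC 0.05, DE = 1 + 3.8 × 0.05 = 1.190 and the error is 7.2%.

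| Scenario | ICC 0.02 | 0.05 | 0.10 | 0.15 |
|---|---|---|---|---|
| m = 4.8, DE | 1.076 | 1.190 | 1.380 | 1.570 |
| m = 4.8, both arms clustered | 5.9% | 7.2% | 9.5% | 11.8% |
| m = 4.8, iCBT only | 5.4% | 6.1% | 7.2% | 8.4% |
| m = 3.8 (76 in 20 groups), both arms | 5.7% | 6.6% | 8.3% | 10.0% |
| m = 3.8, iCBT only | 5.3% | 5.8% | 6.6% | 7.5% |

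**Simulation of H1b under the null** (8,000 runs; 95 per arm in 16 groups, 20% random attrition, complete cases, baseline correlation 0.5, no other covariates, therapist variance 0.02, two therapists, equal ICC in both arms; Monte Carlo error 0.2 to 0.4 points):

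| Model | ICC 0 | 0.02 | 0.05 | 0.10 | 0.15 |
|---|---|---|---|---|---|
| Therapist random, crossed with arm | 5.1% | 6.0% | 7.7% | 9.9% | 12.5% |
| Therapist coded within arm (z test) | 3.1% | 3.4% | 4.1% | 5.5% | 6.4% |
| Group random intercept, 30 df | 3.6% | 3.6% | 4.0% | 4.7% | 5.0% |

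The crossed-therapist model holds its level at ICC 0, so the excess comes from the groups.

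**Multiple imputation** (2,000 runs, 10 imputations, all 95 per arm). When group is left out of both the imputation and the analysis, error is 7.9/9.3/12.6% at ICC 0.05/0.10/0.15, so the excess remains. At a true ICC of 0.15, a group model fitted after imputation without group estimates a mean ICC of 0.102 and has 6.5% error. With group in the imputation, the figures are 0.154 and 5.2%.

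**H3a.** All randomised patients count, so m is 95/16 = 5.94. Simulated logistic models with therapist only (5,000 runs, assumed engagement of 60% or 80%) give 5.8–5.9/7.7–8.3/10.6–11.4/13.0–13.5% at ICC 0.02/0.05/0.10/0.15 with equal clustering, and 5.3–5.9/5.6/6.9–7.6/9.4% with clustering in iCBT only. Group-robust standard errors with 30 df give 4.2–5.1% throughout.

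**The case against.** The harm depends on facts the documents do not give. Being trained for both arms does not establish who leads which group, whether groups are co-led, or how therapist enters the model. If therapist is coded within arm, the simulated error is at or below nominal at low ICC and only modestly above it at 0.15. The ICC range is also assumed, and results run from negligible to large. Six is a maximum: with 4 enrolled and 3.2 analysed per group, the error at ICC 0.02/0.05/0.10 is only 5.5/6.3/7.6% with equal clustering, or 5.3/5.6/6.3% in iCBT only. At 1 month sCBT is part-way through its 12 weeks, so equal ICC in both arms may overstate the problem. The affected tests are secondary or exploratory, and the protocol labels the study a pilot.

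Most of this stands as a limit on size and weight. It does not remove the omission. Therapist could stand in for group only if each therapist led a single group, which does not fit 32 or more groups. If the same interventionists co-lead every group, the therapist term carries no information and group is still missing. The budgeted 1.55 is no answer either: extra patients protect power but do not correct a standard error. One further point is fair: the SAP's imputation rule covers variables in the substantive model, so it calls for group only once group is in that model.

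**Conclusion.** The concern holds. For H1b, H2b and H3a the only cluster level named is therapist, the treatment is delivered in groups, and no group term or group-robust standard error appears in either document. Confidence is high in the omission, not in its size. On the more natural reading of the staffing text (therapist crossed with arm), inflation in H1b and H2b is small at ICC 0.02 (below 1 point by the formula) and material from about 0.05 if both arms cluster. If the budgeted 1.55 was meant for group-sized clusters, it corresponds to ICC 0.11 to 0.145, where equal clustering puts the true error at about 10% to 12%. If it was meant for two therapists, group clustering was never budgeted. Given the secondary and exploratory status of these tests, this should be fixed but does not by itself undermine the trial. For H1a and H2a the finding goes no further than an unstated cluster level.

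**What to change.** - **H1b and H2b:** add a random intercept for assigned therapy group, with Kenward-Roger or Satterthwaite degrees of freedom. Keep the therapist term where it is identifiable; it is not if the same therapists co-lead every group. State how therapist is coded and whether it is crossed with arm.
- **Data:** record the assigned group for every patient randomised to iCBT or sCBT, whether or not the patient attends.
- **Imputation:** carry group into the imputation model, by group indicators or a multilevel step. Once group is in the analysis model, the SAP's own rule asks for this.
- **H3a:** add the group level or use group-robust standard errors. Patients never assigned to a group cannot reach 12 hours, so making each a singleton cluster needs a sensitivity analysis, for example one using the cohort open at randomisation.
- **H1a and H2a:** name the cluster level: group in the active arms, with TAU patients unclustered.
- **G1:** state the ICC and cluster size behind the inflation.

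The cost is SAP wording, one recorded variable, a more complex imputation and somewhat wider intervals. If the group ICC uses up the budgeted 1.55, power for d = 0.57 falls from 79.8% (96 df) to 77.9% (30 df, from 32 groups less 2). Restoring 80% takes about 51.6 effective patients per arm instead of 49. That is 95 × 51.6/49 ≈ 100 randomised, about 5 more per arm. At lower ICC the existing allowance covers it. At very low ICC the group model is slightly conservative, with error of about 3% to 4%.
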